Screening recommendations in each risk category are as described in the Table 3 below. The whole set of recommendations has been elaborated by the steering committee of the trial.

RISK LEVEL ASSIGNMENT MODIFICATION IN RISK-BASED ARM

These risk-based screening recommendations might be subject to evolution during the trial, both at a individual participant level and at the level of the whole trial

At the personal level, a web-based yearly update will be organized for all women in this risk-based arm to better adapt their risk profile if required (only in case off change in family history, personal benign breast biopsy, or identification of a germline high-risk mutation).

At the study level, the re-evaluation will take into account published evidence-based knowledge notably based on SNPs

OTHER MEASURES ASSOCIATED WITH RISK LEVEL

GERMLINE GENETIC TESTING

Of note, for the women identified as having a high-risk family-history, genetic counseling might be advised, according to national and international guidelines. This advice will be part of the recommendations produced by the risk assessment tool. This genetic counseling will be performed in the standard genetic network of the country, and genetic testing for the search of germline BRCA1/2 mutations (or panel testing) usually performed in a cancer-affected relative rather than in the healthy consultant. Such women will of course remain within the trial, and be assigned high or very high-risk categories, with the adequate proposed follow-up.

In Israel specifically, it has been planned that women who have signed a dedicated informed consent (proposed to all participants at study entry) will have an additional evaluation of polymorphisms together with their SNP score, aiming at identifying the presence of one of the three Ashkenazi founder mutations. Such finding will prompt genetic testing for confirmation, as described previously.

BREAST CANCER RISK REDUCTION MEASURES

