1.1.22 Germline genetic testing for high penetrance genes in MyPeBS

While germline deleterious genetic variants of high penetrance genes (BRCA1, BRCA2, TP53, PALB2, PTEN, CDH1, RAD51c, and so on) are rare in general western populations (at most 1 in 500 individuals), three founder mutations of BRCA1 (185delAG and 5382insC), and BRCA2 (6174delT) genes are frequent in the Jewish Ashkenazi population (3% of the population).

Previously identified germline mutation carriers of high-penetrance breast cancer susceptibility gene mutations will not be allowed to enter MyPeBS, given their need of specific screening programs.

Germline mutations of high penetrance susceptibility genes will not be searched systematically in MyPeBS, given their rarity, the complexity of such search and the important risks of harms this would be associated to (high risk of psychological harm given the high frequency of unknown variants, for instance).

However, two situations must be highlighted:

- in MyPeBS, participants for whom a family history compatible with the presence of a high penetrance gene is identified, will be advised a genetic counselling within the national oncogenetic network of each country. In the advent of the identification of a mutation in a high-risk gene, the screening program will be modified accordingly to include yearly mammogram and MRI screening (up to age 60), as recommended in all participating countries.

- in Israeli women, given the prevalence of the three founder mutations of BRCA1 and BRCA2, it appears necessary to propose a pre-identification of these genetic alterations. We will therefore incorporate SNPs dedicated to the identification of these three founder mutations.

However:

- The results of these SNPs will be only provided to women accrued in Israel and who have signed a dedicated specific consent allowing for this identification, after adequate information
- The results of these SNPs will not have any medico-legal value and will only indicate the need for a dedicated genetic counselling and genetic test including proper DNA sequencing towards identification of such germline mutations, if finally present.

In the advent of the identification of one such confirmed mutation, the screening program of the concerned woman (risk-based arm only) will be modified accordingly to include yearly mammogram and MRI screening (up to age 60), as recommended in all participating countries.

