As shown in Fig 1, for women with at most 1 first degree family history of breast or ovarian cancer, risk assessment will be conducted using Mammorisk™ with the implementation of the polygenic risk score results. Mammorisk™ uses age, family history, history of a previous benign biopsy, mammographic density. It evaluates 5-year invasive breast cancer risk using a k nearest neighbor's method. It has been derived from and validated on the Breast cancer Screening Consortium cohort and validated on French screening cohorts. It has previously been used for risk stratification in a national prospective trial. The risk assessment requires adjustment for national breast cancer incidence. Each woman's genotyping results (SNP score) will be implemented into the risk calculation as previously described, for a final risk calculation including SNPs results. As shown in Fig 1, women with more than one first-line first degree relative with breast cancer will have their risk estimated using the Tyrer-Cuzick™ risk score implemented with each person's polygenic risk score as previously described.

Risk evaluation – risk-based arm

Data required for risk assessment

- Clinical and epidemiological characteristics needed for risk stratification will be retrieved from baseline questionnaires filled by participants and their investigator at study entry: age, family history of breast cancer (1st and 2nd degree relatives), personal hormonal and reproductive history, personal history of benign breast disease (with either breast biopsy/FNA and/or surgery), BMI...
- Breast mammographic density evaluation is part of both risk assessment scores.
 - Baseline mammographic density will be that of the most recent mammogram available for the woman
 - Baseline breast mammographic density will be evaluated using a standard procedure as often as possible, i.e. unique validated software provided to MyPeBS' radiologists. If this unique software is not available, radiologists' BI-RADS visual assessment will be used. If no baseline breast mammography is available (women under 50y), the maximum risk will be applied.
- **Genotyping results** will be transmitted by the genotyping lab (CNRGH) to Statlife in a pseudonymized format (tube ID will be the only identifier between these structures)

Risk score assessment

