The individual breast cancer risk will be estimated using the modified Mammorisk™ (by inclusion of SNPs) or, if more than one first degree family history of breast/ovarian cancer, using the modified Tyrer Cuzick™ score, both including polymorphism risk score.

Breast cancer risk levels will to be classified into 4 meaningful categories, which have been defined by the clinical trial steering committee, according to available guidelines and published literature (see 1.1.9).

Statlife is in charge of the centralized and automated software dedicated to risk evaluation. Their module will automatically extract all necessary variables from the central database and incorporate the polygenic score once available, as well as mammographic density.

Statlife will transfer the final risk score of each participant upon availability, to the investigator, who will be in charge of transmitting the result to the participant. The bases of risk calculation will be available on the result

sheet for each participant. The result of the polygenic risk score will also be available and transmitted. Results will be transparently transmitted to allow for awareness and empowerment of participants.

The risk categories estimated using the risk models or identified in other situations, are listed in the Table below.

What if some data is missing?

- If genotyping is not available (failure of technique, participant's refusal), the personal risk will be estimated by the risk score alone (clinical variables + mammographic density)
- If mammographic density is not available:
 - If the participant is 50 years old or more, a baseline mammogram will be mandatory, that will allow density evaluation
 - If the participant is 40-49 years old, the maximum density-linked risk will be applied (BI-RADS class D)
 - If one or two clinical data are not available: risk should be estimated without this information

Risk recalculations

Of note, risk recalculation may occur during the 4-years follow-up of each patient and will be conducted the same way. This may occur if:

- Participant/investigator declares a significant event that may change the participant's risk level (breast biopsy with benign diagnosis, diagnosis of atypical lesion, identification of the participant as a carrier of a germline mutation of a high penetrance gene)

- Identification of a new, major risk polymorphism that would be incorporated in the polygenic risk score

Risk level	Low risk	Average risk	High risk	Very high risk

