Risk model numerical definition (risk score, invasive breast cancer risk at 5 years)	< 1%	1-1.66%	$\geq 1.67\%$ and < 6%	$\geq 6\%$ at 5 years
Other situations	-	-	
 • Any woman diagnosed with an invasive breast cancer during the trial • Any woman diagnosed with an atypical breast lesion or in situ breast carcinoma during the conduct of the study (outside of baseline) 	
 • Israeli women identified as probably bearing a founder gBRCA mutation by SNP assessment • Any woman who appears to be a carrier of a high penetrance susceptibility gene mutation, at any moment during the study (outside of baseline)

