6.2 Safety evaluation

6.2.1 Specific screening-linked safety

In this trial, safety assessments concern some of the secondary endpoints which measure parameters considered as "safety evaluations" since they are linked to screening-related harms:

1. False positive recalls have been defined in the end points and will be carefully scrutinized
2. Overdiagnosis will be estimated
3. The theoretical radiation exposure and potential associated radiation-induced cancer risk will be estimated

6.2.2 **Classical safety:**

Beside these specific screening-linked safety evaluations, no other safety evaluations linked to daily assessments and imaging are planned: as the present clinical trial is totally based on current practices, there is no obligation for any specific AE reporting within MyPeBS.

However, we will take some risk reduction measures for this trial:

- **Breast cancer risk reduction measures in the standard arm**

Participants in the standard arm will be informed on potential risk-reducing strategies. They will be provided written and on-line information material and encouraged on these predefined measures.

Participants will be taught breast self-palpation if they wish so, but this will not be mandatory within the trial.

- **Germline genetic testing**

Of note, for the women identified as having a high family-history, genetic counselling will be advised, according to national and international guidelines. This advice will be part of the recommendations produced by the risk assessment tool. This genetic counselling will be performed in the standard genetic network of the country, and genetic testing for the search of germline BRCA1/2 mutations (or panel testing) usually performed in a cancer-affected relative rather than in the healthy consultant. Such women will of course remain within the trial, and be assigned high or very high risk categories, with the adequate proposed follow-up.

Specifically in Israel, women who have signed a dedicated informed consent will have an additional evaluation of polymorphisms together with their SNP score, aiming at identifying the presence of one of the three Ashkenazi founder mutations. Such finding will prompt genetic testing for confirmation, as described previously.

- **Breast cancer risk reduction measures in risk-based arm**

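### Three sections place women with a high-risk family history in the high or very high category, but the category table has no family-history entry, so a score below 1.67% would make them low or average

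*Protocol*

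**What the plan says.** **The assignment sentence.** The Synopsis, under germline genetic testing, first identifies the group: "for the women identified as having a high-risk family-history, genetic counseling might be advised, according to national and international guidelines". It notes that testing is usually done in an affected relative, and then says: "Such women will of course remain within the trial, and be assigned high or very high-risk categories, with the adequate proposed follow-up". Section 5.2.7 has the same sentence. Section 6.2.2 has it too, with one hyphen fewer: "Such women will of course remain within the trial, and be assigned high or very high risk categories, with the adequate proposed follow-up".

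**The category table.** Section 5.2.3 introduces its table with: "The risk categories estimated using the risk models or identified in other situations, are listed in the Table below". The score row is headed "Risk model numerical definition (risk score, invasive breast cancer risk at 5 years" and sets low below 1%, average 1 to 1.66%, high from 1.67% to below 6%, and very high from 6%. The row of other situations places in the high category women diagnosed during the trial with invasive cancer, an atypical lesion or in situ carcinoma. It places in the very high category Israeli women with a probable founder mutation and "Any woman who appears to be a carrier of a high penetrance susceptibility gene mutation, at any moment during the study". Family history appears in neither cell. The threshold tables in the Synopsis and in sections 1.1.9, 3.1.4 and 5.2.5 have no family-history route either.

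**Section 1.1.22.** A family history compatible with a high-penetrance gene leads to advice to seek counselling. Then: "In the advent of the identification of a mutation in a high-risk gene, the screening program will be modified accordingly".

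**The concern.** The category determines what a woman is offered for four years. In section 5.2.5, low risk means no mammogram until the end of the study, high risk means one every year, and very high risk adds annual MRI until age 60. A rule that gives the same woman two categories therefore gives her two schedules.

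The category also sets the compliance rule in section 8.3.1, and so membership of the per-protocol population used for the primary non-inferiority analysis. It further decides who belongs to the low-risk group whose cancers are notified and reviewed under sections 12.2 and 12.3.

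**Working it through.** No formula applies to the contradiction itself; the check sets the passages side by side.

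**1. Is the assignment conditional?** No. In all three places it attaches to women identified as having such a family history. No score threshold or mutation result is mentioned, and the choice between high and very high is left open.

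**2. Does the table contain the rule?** No. Without one of the listed events, only the score row applies.

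**3. Does the score guarantee a high result?** Not on the protocol's own account.
- High-risk family history is not defined, so it cannot be equated with the Tyrer-Cuzick trigger of more than one first-degree relative. A woman with at most one is scored with Mammorisk.
- Section 1.1.8 says that adding the polygenic score moves women to lower as well as higher categories.
- Section 1.1.15 expects 60% of women aged 40-49 to be low risk, so low scores will be common at the ages where a family history may be most prominent.

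**4. Does section 1.1.22 decide the matter?** No. It names counselling and, once a mutation is found, a changed programme. It gives no category before or without a mutation.

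**5. What follows for a woman with such a history and no identified mutation?** The compliance counts are those of section 8.3.1, over 4 years, outside baseline and end-of-study mammograms.

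| 5-year score | By the table | Count required | By the sentence | Count required | Counts that meet both |
|---|---|---|---|---|---|
| below 1% | low | at most 1 | high | at least 2 | none |
| below 1% | low | at most 1 | very high | at least 3, plus at least 3 MRIs | none |
| 1-1.66% | average | at least 1 and under 4 | high | at least 2 | 2 or 3 |
| 1-1.66% | average | at least 1 and under 4 | very high | at least 3, plus at least 3 MRIs | 3 (with the MRIs) |
| 1.67% to below 6% | high | at least 2 | high or very high | as above | no conflict if high is meant |

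The rows are mutually exclusive only below 1%. For average scores they overlap.

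**6. Size.** The protocol gives no count of women with such a history, nor their score distribution. A scale can be set from its own rate. At 120 per 100,000 per year over 4 years, expected stage 2+ events are 0.0012 × 4 = 0.0048 per woman, or 4.8 per 1,000 affected women. Against the 298 events required, 4.8 / 298 = 1.6%. If the rate in these women were double the average (an assumption), the figures would be 9.6 events and 9.6 / 298 = 3.2%. The 1,000 is a unit of scale, not an estimate.

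**The case against.** The strongest reply is that the sentence is not a classification rule. It closes a paragraph on counselling that opens as a side note, and may only describe where such women are expected to end up: high on their score, very high once a mutation is confirmed. Classification is done centrally by one automated module, family history enters through the score, and a change in family history is a stated reason to update the risk profile. Nothing shows sites choosing between rules. This is a fair reading of intent, but the text says that these women are assigned the category, and the scoring rules do not ensure that result.

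Other limits also stand:
- **Section 1.1.22.** A reader might infer that it moves women only after a mutation is found, and so contradicts the assignment sentence. It does not say only, and high before testing with very high afterwards would satisfy both.
- **Completeness of the table.** Section 5.2.3 does not say that the table lists every situation. The conflict rests on the missing entry, not on a claim of completeness.
- **Compliance.** A reader might infer that women will be dropped from the primary set for following the other rule. Section 8.3.1 judges compliance with the recommendation a woman was given. Her status comes into doubt only if the category issued and the category used in the analysis come from different readings.
- **Eligibility.** Non-inclusion criterion 3 (section 4.2) excludes women with a known or suspected very high-risk predisposition. Depending on how suspicion is applied, it may remove many of the strongest family histories. The Synopsis still provides for such women as participants.
- **Model choice.** One sentence in section 5.2.3 says "women with more than one first-line first degree relative with breast cancer will have their risk estimated using the Tyrer-Cuzick", without ovarian cancer. A reader might infer that a woman with one breast and one ovarian relative fits neither model. The Synopsis, the later paragraph on risk score assessment and the preceding Mammorisk sentence all count breast or ovarian cancer. This is a wording slip, not a gap in the algorithm, and the figure showing the algorithm is not available here.

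**Conclusion.** The inconsistency is real but narrow. The assignment sentence in the Synopsis and sections 5.2.7 and 6.2.2 does not agree with the category table in section 5.2.3 for women with a high-risk family history, no identified mutation and a score below 1.67%. Below 1%, the two readings give incompatible schedules and mutually exclusive compliance rows; between 1% and 1.66%, the schedules differ but the rows overlap.

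The number of women affected cannot be derived from the protocol. The effect on the primary analysis is probably small, given the events-per-1,000 scale above and the possible narrowing by criterion 3. The documents do not support a claim that the primary result is threatened. The matter deserves correction because it concerns which screening schedule an individual woman is offered, and because correcting it is cheap.

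**What to change.** Reconcile the sentence in the Synopsis and sections 5.2.7 and 6.2.2 with the category table in section 5.2.3, and with section 1.1.22, so that a single statement says whether family history alone sets a category and, if so, which one. If it does, define the family history meant and enter it in the table. If it does not, remove or reword the sentence. Have the risk module and the per-protocol row in section 8.3.1 follow the category so assigned.

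As a minor wording point, bring the breast-only phrase in section 5.2.3 into agreement with the Synopsis and the rest of that section.

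Which classification rule is right is for the sponsor and the Clinical Trial Steering Committee; none is proposed here. The cost is protocol wording and a check of the risk-module specification, with no new data or visits.

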1. INTRODUCTION

MyPeBS addresses the crucial and timely question of the future of breast cancer screening in Europe. Indeed current standard mammographic screening, with entry stratified by age alone, has recently been largely questioned. Despite a demonstrated mean 20% reduction in breast cancer-specific mortality, together with reduction of late-stage disease in women older than 50, mammographic screening is associated with potential harms including false positive recalls and over-diagnosis.

Individual breast cancer risk estimation, through combined risk scores including clinical variables, mammographic breast density and more than 100 genetic polymorphisms, now has substantial clinical and scientific bases. Personalized screening strategies, based on individual risk levels, could potentially improve the individual benefit/harms ratio of screening (earlier cancer detection and less intensive treatments in high risk women, less false positives and over-diagnoses in low risk ones), and increase the cost-efficacy for health insurances [Hood 2011, Burton 2013, Cox 2014, Gagnon 2016, Lee 2017].

MyPeBS will conduct an international randomized study to validate this hypothesis. It will primarily assess the ability of an individual risk-based screening strategy to be non-inferior, and possibly superior, to the standard of care screening, in reducing the cumulative incidence of stage 2+ breast cancers. The study, conducted in 5 countries (France, Italy, UK, Belgium, and Israel) will include 85,000 European women aged 40-70 years, all followed for 4-years. MyPeBS will also evaluate if an individual risk-based screening strategy, compared with the standard screening, reduces screening-related harms such as unnecessary biopsies, overdiagnosis in low-risk women, is overall at least as cost-effective as well as more accepted by women resulting in a larger screening coverage. After analyses of all components, the final objective of MyPeBS is to deliver the best recommendations for the best future breast cancer screening strategy in Europe.

1.1 Study rationale and justification

1.1.1 Current status of breast cancer in western countries

Breast cancer is the most common cancer and the second leading cause of cancer death among women in Western countries. Breast cancer (BC) is a dramatic worldwide issue with almost 1.7 million new BC diagnoses and 521,900 BC deaths estimated worldwide in 2012 <https://www.ncbi.nlm.nih.gov/pubmed/28376154>.

Breast cancer remains a potentially lethal disease. Indeed, 20 to 25% of women developing breast cancer will eventually die, due to the development of metastases. Risk of metastases and global prognosis are linked to both tumor biology and burden at diagnosis (Cardoso 2016).

Although very long survivals are sometimes possible, metastatic breast cancer remains an incurable disease. The median survival after diagnosis of metastases currently ranges from 14 months (triple-negative breast cancers) to 56 months (Her2-positive breast cancers) (Gobbini 2018).

Localized breast cancer currently most of the time still requires aggressive and prolonged treatments associated with long-term consequences (Azim 2011). Treatment intensity and heaviness is clearly deeply linked to the cancer's biology, but also to tumor burden at diagnosis. Tumor burden is the major determinant of the extent of the local therapies, including surgery (partial versus complete mastectomy, axillary surgery) and radiation therapy. Adjuvant medical treatments for breast cancer, including chemotherapy, endocrine and targeted therapies remain difficult for women; they are associated with long-term sequelae, and represent high management costs (Azim 2011).

There is therefore a major need for prevention, including earlier diagnosis (associated with a better prognosis, less treatments needs, less morbidity from the therapies, and lower costs) through secondary prevention, but also, of course, primary prevention.

1.1.2 **Current breast cancer screening in western countries: benefits and potential harms, evaluation, organization**

Current breast cancer screening policies in western countries and known benefits

In Western countries, breast cancer screening is part of national organized screening systems with monitoring of screening quality and with double reading (except in Israel) of the mammograms. Certified radiologists and radiographers are responsible for quality of the diagnostic performance.

Apart from very rare patients at very high-risk, age is currently the only criterion for starting screening. Depending on the country, mammograms are offered every 1 to 3 years, starting from the age of 40-50 years up to 69-74 years.

These screening recommendations are based on large-scale randomized studies (New York, Malmo 1 and 2, Edinburgh, Swedish 2 county, Canada trials 1 and 2, Stockholm, Goteborg, UK age trial) that have globally shown that screening reduced breast cancer specific mortality by about 20% in the intent-to-treat populations (invited women), or 30-40% in the per-protocol populations (participating women).

Several reappraisals of these mammographic screening-associated benefits in the randomized trials have been published in the past 10 years with variable interpretation of data. Indeed, trials' methodologies are somehow heterogeneous most trials dated at times incidence and therapies were quite different. The UK independent panel estimated the benefit of mammographic screening starting at age 50 to be in the range of one breast cancer death prevented for 250 women invited (Marmot et al, 2011).

The benefit and risk-benefit ratio of mammographic screening between the age of 40 and 50 is controversial and each country currently has its own policy. Mammographic screening has also been demonstrated to reduce the number of stage 2 and higher cancers at diagnosis in women older than 50.

Current breast cancer screening by mammography: harms and weaknesses

8,18,87,97,107,127,161,125,128,109,136,161

Current screening by mammography is associated with a number of harms or weaknesses that have been largely debated in the medical literature in the past 10 years:

1. The sensitivity of 2-yearly and furthermore 3-yearly mammogram is not optimal: 1-2 (or more for UK) breast cancers every 1,000 examined women are interval cancers (Blanch, Mandelson, Houssaimi 2017). This turns to 16 to 35% of cancers being interval cancers according to the screening interval. Furthermore, about one fourth of the cancers occurring in regularly screened women are still diagnosed at stage 2 or more.
2. A small percentage of screening mammograms lead to additional check-ups or biopsies for an image that turns to finally be benign: these "false positive" results, according to the way they are estimated concern 3-14% (3% being only cases where biopsies are recommended, whereas higher rates are observed if additional US is considered a check-up) of all screening mammograms (Gøtzsche and Nielsen, 2011; Pace and Keating, 2014; Anon, 2017), causing useless patient's anxiety (Brodersen and Siersma, 2013; Nelson et al., 2016; von Euler-Chelpin et al., 2016).
3. Another criticism is overdiagnosis (screen detection of a cancer that would not have become clinically apparent without screening) which is estimated in average as 10% of all screen-detected cancers (estimates are highly variable; they range from 1% to 30%, depending on the population and estimation methods), leading to an inherent overtreatment.
4. Mammographic screening is associated with a risk of radio-induced breast cancer. This risk appears extremely low (about 1 in 1,000 women screened during 30 years) compared to the benefits of early diagnosis and radiation doses delivered are now very closely monitored. The most pessimistic evaluation of this risk in US women undergoing yearly mammogram from age 40 has led to the following conclusions

(Miglioretti 2016): On average, annual screening of 100,000 women aged 40 to 74 years was projected to induce 125 breast cancers (95% confidence interval [CI]=88–178) leading to 16 deaths (95% CI=11–23) relative to 968 breast cancer deaths averted by early detection from screening. Women exposed at the 95th percentile were projected to develop 246 radiation-induced breast cancers leading to 32 deaths per 100,000 women. Women with large breasts requiring extra views for complete breast examination (8% of population) were projected to have higher radiation-induced breast cancer incidence and mortality (266 cancers, 35 deaths per 100,000 women), compared to women with small or average breasts (113 cancers, 15 deaths per 100,000 women). Biennial screening starting at age 50 reduced risk of radiation-induced cancers 5-fold.

Participation rates

Beside these elements, another problem faced by western countries are the variable participation rates to national organised screening programs: indeed, to be efficient at a public health levels, this type of intervention requires a high (70% or more) participation. Some western European countries or regions currently face decreasing and quite low participation rates (25-30%).

Routine screening guidelines and protocols in the participating countries

In MyPeBS, breast cancer screening activities and breast density assessments follow current updated European and national guidelines regarding methods and indications in the standard arm as well as, while in the exploratory risk-based arm, except regarding screening intervals for the latter.

- European guidelines (standard, good practice, equipment, quality assessments)

We have ensured, and will monitor during the trial, that all screening activities in the standard arm will follow the current European Commission breast cancer screening guidelines (2006 and update 2016) (<http://www.euref.org/european-guidelines>, and <http://ecibc.jrc.ec.europa.eu/-/european-guidelines-for-breast-cancer-screening-and-diagnosis-the-european-breast-guidelines>) and the European Society of Breast Imaging (EUSOBI) recommendations (<http://appliedradiology.com/articles/european-society-of-breast-imaging-s-recommendations-on-breast-cancer-screening>)

The European commission initiative on breast cancer (ECIBC) has developed guidelines platform for all breast cancer processes as well as for quality assessments (several members of the consortium have participated to these initiatives), and we will refer to them and use them as standard throughout the study: <http://ecibc.jrc.ec.europa.eu/-/the-ecibc-guidelines-platform-for-all-breast-care-processes>
<http://ecibc.jrc.ec.europa.eu/documents/20181/22500/EC+Initiative+on+Breast+Cancer.pdf/a586dfb5-83d2-4ee3-a345-9ddf72363fa8>

- National guidelines

In the standard arm of MyPeBS, breast cancer screening has to comply with the current ongoing national guidelines and procedures, while they will follow the same except for screening intervals, in the exploratory arm:

UK: <https://www.gov.uk/government/collections/breast-screening-professional-guidance>

Italy: http://www.ccm-network.it/screening/files/documenti/raccomandazioni_linee_guida.pdf, and http://www.ccm-network.it/screening/files/documenti/raccomandazioni_linee_guida.pdf ,

Israel: http://en.cancer.org.il/template_e/default.aspx?PagelId=7749

Belgium: <https://www.ccref.org/old/pdf/MB25112000.pdf>; <https://www.ccref.org/old/pdf/MB10082001.pdf>; and Royal decree establishing the necessary standards for the accreditation of specialist breast cancer centres in Belgium – January 1st 2008.

France: http://www.has-sante.fr/portail/jcms/c_1741170/fr/depistage-du-cancer-du-sein-en-france-identification-des-femmes-a-haut-risque-et-modalites-de-depistage, <http://www.e-cancer.fr/Professionnels-de-sante/Depistage-et-detection-precoce/Depistage-du-cancer-du-sein/Orienter-vos-patientes>)

The current national/European guidelines in use may vary during the trial, at a national or European level. Guidelines and procedures in the standard arm will be updated accordingly and timely.

All participating countries have specific guidelines for:

- **High-risk women** defined as having had a previous breast cancer or high-risk situations including radiation therapy for Hodgkin's disease or atypical hyperplasia. These women will not be eligible for MyPeBS
- **Very high-risk women** defined as having a germline mutation of either BRCA1 or BRCA2 genes or an equivalent situation. These women will not be included in MyPeBS

1.1.3 “4P medicine” and application to breast cancer screening

Personalized cancer prevention approach (meaning personalized risk assessment together with specific individual screening and primary prevention) is a major public health challenge. However, this approach needs individual risk identification, adequate perception and awareness leading to changes in behaviors towards cancer prevention. It also requires reaching the adequate population and avoiding disparities in health care access. This is included in the so-called P4 medicine (Predictive, Personalized, Preventive, and Participatory) (Hood 2011).

Risk based prevention is highly efficient in other public health models

Several models of the public health impact of risk-based prevention exist, such as in infectious diseases or neonatology. A major model of the medical, sociological and economical efficacy of risk-based prevention (including screening and interventional prevention) is that of cardiovascular diseases. In this setting, computational approaches have led to combine risk factor information for a better individual prediction, and the early development of 10-year absolute cardiovascular risk "Framingham" model designed for routine clinical practice, in 1998. These advances have led to major improvements in specific survival and global survival of the identified individuals, together with eviction of unnecessary interventions among those at low risk. Current guidelines recommend the use of algorithms for cardiovascular risk assessment that combine information of age, sex, together with traditional risk factors (blood pressure, lipids, and smoking), along with other emerging biological factors. Since environmental exposures have a major role to play, constitutional genetics have not yet become a major player in this setting outside of family history.

Proof of concept of breast cancer risk-based screening in very high-risk women

Personalized screening has so far only been used as more intensive screening for very high-risk individuals bearing germline predisposition mutations (mostly of BRCA1/2 until recently). Intensive breast screening, including yearly mammogram and MRI starting at a young age (25-30), have proven to be efficient in these women in terms of drastic reductions in cancer stage at diagnosis and projected reductions in breast cancer-specific mortality. Of note, risk reduction strategies have also proved to be effective for such individuals identified to be at very high hereditary risk of breast cancer. Beside this, women with a past history of breast cancer, atypical lesions or chest wall radiation therapy are also currently identified to be at higher risk of

subsequent breast cancer. National and international guidelines recommend that these women receive increased screening and other prevention measures, which are associated with some suggested benefits.

Modeling of potential benefits of risk based screening in the general population (Yen, Hall, Koitsatu, Onega, Morman)

The vast majority of women is not at increased risk of breast cancer and is recommended to follow general screening guidelines. Only 1 in 9 of these average-risk women will ultimately develop breast cancer. Developing more effective, risk-based screening approaches for this general population requires validated risk-estimation models and assessment of the clinical usefulness of such models. Risk-based screening has indeed recently been recognized by many societies or groups, as a major way to be explored for its ability to lead to a better screening, which would be more effective, less morbid, and health-economically beneficial.

In the absence of randomized controlled trials evaluating the efficacy of risk-based screening protocols in the general population, simulation modeling studies have provided insight into the potential risk/benefit balance of different risk-based screening protocols. These modeling studies suggest that screening regimens should be personalized based on a woman's age, breast density, and other risk factors. One study used several established CISNET (NCI-funded Cancer Intervention and surveillance Modeling Network) simulation models to determine the most efficient screening strategies based on individual breast cancer risk. Biennial screening appeared as the most efficient strategy for most women who are at average risk of breast cancer.

However, for women with 2-fold to 4-fold increase in risk, annual screening beginning at age 40 years had comparable risks and benefits with those of women at average risk undergoing biennial screening between ages 50 and 74 years. Another CISNET study found that women aged 40 to 49 years with a 2-fold increased risk have similar harm/benefit risk ratios compared with average-risk women aged 50 to 74 years undergoing biennial screening.

